10.7 Events Not to Be Considered as AEs/SAEs

Medical conditions that are present at the initial study visit that do not worsen in severity or frequency during the study are defined as Baseline Medical Conditions and are NOT to be considered AEs. Progression of underlying disease is not an AE and therefore not an SAE per se, rather an efficacy end-point, unless deemed to be causally related to administration of IPs. However, if adverse signs or symptoms occur in association with disease progression then these should be recorded as AEs and reported as SAEs if meeting any seriousness criteria.

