10.8 Methods of Recording and Assessing Adverse Events

At each study visit, the subject will be queried on changes in his/her condition. During the reporting period of the study any unfavorable changes in the subject's condition will be recorded as AEs, whether reported by the subject or observed by the Investigator.

Complete, accurate and consistent data on all AEs experienced for the duration of the reporting period (defined below) will be reported on an ongoing basis in the appropriate section of the CRF. Among these AEs, all SAEs must be additionally documented and reported using an AE report form. It is important that each AE report include a description of the event, its duration (onset and resolution dates (/times "/times" to be completed when it is important to assess the time of AE onset relative to the recorded treatment administration time)), its severity, its relationship with the study treatment, any other potential causal factors, any treatment given or other action taken (including dose modification or discontinuation of the IPs) and its outcome. In addition, serious cases should be identified and the appropriate seriousness criteria documented. Specific guidance can be found in the CRF completion and monitoring conventions provided by the Sponsor.

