10.9 Adverse Event Reporting Period

The AE reporting period for safety surveillance begins when the subject is included into the study (date of first signature of informed consent) and continues through the study's post-treatment follow-up period, defined as 30 days from the final administration of the study treatment or immediately before initiation of any other anticancer therapy, whichever comes first.

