11 STUDY PROCEDURES

11.1 Screening and Baseline Assessments

A signed Informed Consent Form (ICF) must be obtained before any study-specific screening evaluations are performed and should be documented in the subject's medical chart.

The following evaluations and procedures will be performed within 28 days prior to the first study drug administration (Cycle 1 Day 1). Any screening evaluation, including disease status, will need to be repeated if performed more than 28 days from Cycle 1 Day 1. Evaluations performed as part of the standard of care within 28 days of dosing but prior to consent, do not need to be repeated. By signing the consent form, the subject agrees to the collection of this health information.

- Obtain signed ICF and form for the HIPAA/Data Protection Act
- Record subject's medical history, including demographics, primary diagnosis and WHO
 classification (Table 8), outcome and duration of response to prior cancer therapy and any
 ongoing AEs
- Record the number of RBC, whole blood and platelet transfusions for the 4 months prior to Cycle 1 Day 1.
- Record concomitant medications
- Record subject height

- Perform hematology tests: hemoglobin, reticulocytes, platelets, WBCs, neutrophils, neutrophil precursors (promyelocytes, myelocytes, metamyelocytes, band neutrophils), monocytes, lymphocytes and blasts. Hematology tests must be performed ≥ 1 week prior to Cycle 1 Day 1.
- Perform serum chemistry laboratory tests (AST, ALT, total bilirubin, creatinine, BUN, potassium and calcium). Subjects are not required to be fasting.
- Perform coagulation tests (APTT, PT/INR)
- Perform bone marrow aspirate for disease assessment,
 If the bone marrow aspirate is inadequate, a bone marrow biopsy should be performed.

The following evaluations and procedures will be performed within 14 days prior to the first administration of study drug (Cycle 1 Day 1):

- Record subject weight
- Collect vital signs (heart rate, blood pressure, temperature)
- Complete physical examination
- Assess ECOG performance status.

The following evaluation and procedure must be performed within 72 hours prior to the first administration of study drug (Cycle 1 Day 1):

Perform urine or serum pregnancy test for females of child-bearing potential only

Laboratory assessments may be repeated if values are borderline to inclusion level or may change due to best supportive care measures.

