If the subject meets all eligibility criteria after the screening visit(s), the study site will request an assigned subject number and treatment assignment from the Sponsor or designee.

11.2 Day 1 of Cycle 1

The following assessments will be conducted before the first dose of tipifarnib on Day 1 of Cycle 1:

- Record any RBC, whole blood and platelet transfusions that were received between the screening visit and Cycle 1 Day 1.
- Record concomitant medications
- Assessment of AEs
- Assess ECOG performance status.
- If not collected within the 14 days prior to Cycle 1 Day 1 as specified in Section 11.1, record subject's weight and vital signs
- Symptom based physical examination
- Perform serum chemistry laboratory tests (AST, ALT, total bilirubin, creatinine, BUN, potassium and calcium). Subjects are not required to be fasting. Serum chemistry tests do not need to be repeated on Cycle 1 Day 1 if the screening laboratory tests were conducted within 72 hours prior to the first dose of tipifarnib.
- Perform hematology tests: hemoglobin, reticulocytes, platelets, WBCs, neutrophils, neutrophil precursors (promyelocytes, myelocytes, metamyelocytes, band neutrophils), monocytes, lymphocytes and blasts.

Subjects will self-administer the first dose of tipifarnib with food in the evening. On Day 1 of Cycle 1, only 1 dose of tipifarnib will be administered. Thereafter, subjects will continue to self-administer tipifarnib twice a day (approximately every 12 hours, same time every morning and evening, with food) based on their assigned dose regimen. The interval between dosing should not be less than 6 hours.

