12.2.2 Safety and Tolerability

Safety and tolerability of tipifarnib will be assessed based on the following:

- Incidence, duration, and severity of TEAEs, SAEs, AEs resulting in permanent discontinuation of study drug, and deaths within approximately 30 days from the last dose of study drug (or immediately before the administration of another anticancer treatment)
- Changes in laboratory test results

AEs will be coded using the latest available version of the Medical Dictionary for Regulatory Activities (MedDRA). TEAEs are defined as AEs that start on or after the first dose of study

drug and within approximately 30 days of the last administration of study drug. AEs will be summarized by the number and percentage of subjects who experienced the event, according to system organ class and preferred term. A subject reporting multiple cases of the same AE will be counted once within each system organ class and similarly counted once within each preferred term

Unless specified otherwise, the denominator for these calculations will be based on the number of subjects in each cohort who received at least one administration of tipifarnib, irrespective of the total number of doses or treatment cycles administered. These conventions will be appropriately modified to calculate AE incidence rates separately for each cycle that study therapy is administered. AE incidence rates may also be calculated based on other measures of subject exposure (e.g., total number of treatment cycles administered). AEs will also be summarized by NCI CTCAE v.4.03 severity grade, by relationship to each study drug and by treatment regimen. Additional summaries may also be provided for SAEs, and events resulting in the permanent discontinuation of therapy. All AEs will be included in individual subject listings.

The incidence of grade 3 and 4 hematological toxicities (including neutropenia, thrombocytopenia, and anemia) will be provided by treatment cycle and across all treatment cycles. The toxicity grades for laboratory tests will be based on NCI CTCAE v.4.03 criteria. The use of blood transfusions (platelets, red blood cells, whole blood) and/or growth factor support will be reported.

Vital sign results (heart rate, blood pressure and temperature) will be summarized descriptively for each scheduled and unscheduled protocol time point. Changes will be calculated relative to the assessments at baseline.

Sample Size Determination

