10.1. Adverse Events

Adverse events will be coded using the latest available version of the Medical Dictionary for Regulatory Activities (MedDRA). Treatment-emergent adverse events are defined as AEs that start on or after the first dose of study drug and within approximately 30 days of the last administration of study drug. AEs will be summarized by the number and percentage of subjects who experienced the event, according to SOC and PT. A subject reporting multiple cases of the same AE will be counted once within each SOC and similarly counted once within each PT. For summaries by maximum severity, each subject will be counted only once under the most severe event.

Unless specified otherwise, the denominator for these calculations will be based on the number of subjects who received at least one administration of tipifarnib regardless of the total number of doses or treatment cycles administered. These conventions will be appropriately modified to calculate AE incidence rates separately for each cycle that study therapy is administered. AE incidence rates may also be calculated based on other measures of subject exposure (e.g., total number of treatment cycles administered). For subjects enrolled prior to Protocol Amendment 3, their AE counts will only be provided in the Total column (Regimen 1 + Regimen 2 + Original Cohort). Regimen 1 and Regimen 2 subjects will be presented separately and in the Total columns.

AE durations will be calculated using all TEAEs. For any AE that is still ongoing at the end of study, we will use the last contact date as the end of AE stop date for calculation the duration of AEs. Median, minimum and maximum of AE durations will be reported.

AEs will also be summarized by NCI-CTCAE version 4.03 severity grade and by relationship to each study drug. Additional summaries may also be provided for SAEs, and events resulting in the permanent discontinuation of therapy. All AEs will be included in individual subject listings.

Hematologic abnormalities reported as AEs that were coded to preferred terms in the Investigations SOC have been pooled with appropriate terms in the Blood and Lymphatic System SOC for tabulation for the following categories:

- Platelet count decreased = Thrombocytopenia;
- Neutrophil count decreased = Neutropenia;
- White blood cell count decreased = Leukopenia;
- Lymphocyte count decreased = Lymphopenia.

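### The TEAE definition uses start date alone, so a clinical AE that opens before first dose and worsens on tipifarnib drops out of the TEAE tables if the site keeps one record

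*SAP*

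**What the plan says.** Both documents define treatment emergence by when an event begins. SAP 10.1: "Treatment-emergent adverse events are defined as AEs that start on or after the first dose of study drug". Protocol 12.2.2: "TEAEs are defined as AEs that start on or after the first dose". Each also sets an upper limit of roughly 30 days after the last dose, and neither mentions worsening.

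AE collection starts earlier than dosing. Under Protocol 10.9 the reporting period "begins when the subject is included into the study (date of first signature of informed consent". The main screening procedures "will be performed within 28 days prior to the first study drug administration" (Protocol 11.1), and AE assessment is on the pre-dose list in Protocol 11.2: "The following assessments will be conducted before the first dose of tipifarnib on Day 1 of Cycle 1".

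On worsening, Protocol 10.7 exempts from AE status "Medical conditions that are present at the initial study visit that do not worsen in severity or frequency during the study". Protocol 10.8 says that "any unfavorable changes in the subject's condition will be recorded as AEs", and then defers the detail: "Specific guidance can be found in the CRF completion and monitoring conventions provided by the Sponsor". Those conventions are not among the documents.

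**The concern.** An event can begin after the initial visit, be open at first dose, and get worse on drug. If the site updates the existing record, the onset date stays before dosing and the event fails the stated rule, although the worsening is exactly what a treatment-emergent summary is meant to show.

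For example, Grade 1 diarrhea begins a week after the screening visit and becomes a non-serious Grade 3 event on treatment, judged related. Held as one record, it is missing from the drug-related Grade 3 or higher table and from the maximum-severity table. If it led to withdrawal, that withdrawal would be counted in the disposition and drug-modification summaries (SAP 8.1, 8.4) but not by SOC and PT in the table of TEAEs leading to discontinuation.

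AE counts are shown separately by regimen, and Protocol 9.4 says the study's data will inform the choice of dose and regimen. No formal tolerability test is planned, so the consequence is descriptive.

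**Working it through.** The plan gives no figure to reproduce. The check applies the definition to a case and then sizes one misclassified subject.

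**Step 1. Can a pre-dose AE record exist?** Yes. Collection runs from consent (Protocol 10.9), the screening window is up to 28 days (11.1), and AEs are assessed again before the first dose (11.2).

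**Step 2. Does the baseline-condition rule capture it?** No. Protocol 10.7 concerns conditions present at the initial visit, which become AEs only when they worsen. A worsening after first dose then naturally carries a post-dose onset. An event that begins between that visit and first dose is already an AE and lies outside that rule.

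**Step 3. Apply the TEAE rule.**

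| How the site records the worsening | Onset date in the data | TEAE under SAP 10.1? |
|---|---|---|
| New record at the grade change | After first dose | Yes |
| Original record updated | Before first dose | No |

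**Step 4. Which SAP 10.1 outputs are labelled as TEAE?** Incidence by SOC and PT, incidence by maximum severity, duration, drug-related TEAEs, drug-related TEAEs of Grade 3 or higher, and TEAEs leading to permanent discontinuation. In the second row above, the event is absent from all of these. Some other summaries and overview items in SAP 10.1 refer only to AEs under a TEAE overview, so their scope is unclear.

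**Step 5. What is covered elsewhere?**
- Laboratory worsening: the shift table in SAP 10.2.
- Serious events: the SAE table in SAP 10.1, which is not worded as TEAE-only. Non-laboratory Grade 4 and 5 events must be reported as SAEs (Protocol 10.3), so they reach it too.
- Withdrawals: the counts in SAP 8.1 and 8.4.
- Every AE: the subject listings.

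What remains is mainly non-serious clinical AEs of about Grade 2 to 3.

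**Step 6. Size of one affected subject.** The change in a term's incidence is 1/N, and it occurs only if the subject has no other post-dose record of that term. Inputs: 11 per cohort in Stage 1 and 18 per full cohort (SAP 5), hence 22 and 36 over both cohorts. The Original Cohort is at least the first 9 subjects, enrolled before Amendment 2 (Protocol 9.4). All are assumed dosed.

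| Column | N | 1/N |
|---|---|---|
| Regimen, Stage 1 only | 11 | 9.1 points |
| Regimen, full cohort | 18 | 5.6 points |
| Total, both cohorts stop at Stage 1 | 22 + 9 = 31 | 3.2 points |
| Total, both cohorts fill | 36 + 9 = 45 | 2.2 points |

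The SAP's Original Cohort is everyone enrolled before Amendment 3, so 9 is a lower bound and the Total-column figures are upper bounds for those two scenarios. The documents give no rate for such events, so the total effect cannot be computed.

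**The case against.** The strongest reply is that the single-record premise is unproven and that the visible text leans against it. Protocol 10.8 has subjects queried at every visit and any unfavorable change recorded as an AE, and a move from Grade 1 to Grade 3 is such a change. Protocol 9.11 requires a worsening treated with concomitant therapy to be reported on the AE form. The unseen CRF conventions may already split records at a grade change. This carries weight: it is why the point is conditional and why the effect may be nil. It does not dispose of the point, because neither section says that worsening of an open AE gets a new record with a new onset date. Both are satisfied by updating the existing one.

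A second reply is that little can be lost. The event must be non-laboratory, non-serious and below Grade 4, begin in a window of about 28 days, and still be open at first dose. It also remains in the listings, and a safety monitoring committee reviews safety data regularly (Protocol 10.2). That is correct and sets the severity. Still, a listing does not restore an event to an incidence table.

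A third is that 9.1 points is not a true maximum, because Protocol 8.5 allows the study to stop for poor enrollment and a cohort could then be smaller than 11. That stands; the figures apply to cohorts that reach the planned sizes.

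**Conclusion.** The concern holds, as a minor point. As written, the rule excludes a pre-dose AE that worsens on drug whenever the worsening stays under the original record. Compared with a start-or-worsen rule, the number of subjects counted with a TEAE can only be equal or lower. The number affected is unknown, and is zero if the CRF conventions split records at a grade change. The one-subject figures are arithmetic for scale and not a forecast. They assume cohorts of the planned size, all subjects dosed, and no other post-dose record of the same term. The ORR analysis, the stage decision, alpha and power do not depend on this definition. Confidence is medium, because the recording conventions cannot be seen.

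**What to change.** In SAP 10.1 and Protocol 12.2.2, define a TEAE as an AE that starts, or increases in CTCAE grade from its pre-dose level, on or after the first dose and within approximately 30 days of the last dose. Date the worsening at the grade change, and use that date and the post-dose grade in the TEAE summaries.

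The cost is one clause in each document, a CRF completion note and minor programming. Sites must date grade changes, and reported TEAE rates may rise slightly. If the CRF holds only one severity per record, subjects already enrolled could need retrospective queries for AEs open at first dose. If records are already split at a grade change, no count changes.

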7.5. Handling of Dropouts or Missing Data

Where individual data points are missing because of insufficient samples, dropouts, or other reasons, the data will be analyzed based on reduced denominators. For survival analysis, dropouts without confirming events will be treated as censored.

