10. SAFETY ANALYSES

Safety and tolerability of tipifarnib will be assessed based on the following:

- Incidence, duration and severity of TEAEs, SAEs, AEs resulting in permanent discontinuation of study drug, and deaths within approximately 30 days from the last dose of study drug (or immediately before the administration of another anti-cancer treatment)
- Changes in laboratory test results
- Serum Chemistry: Blood Urea Nitrogen, Creatinine, Potassium, Calcium, Total Bilirubin, ALT, AST
- Hematology: White Blood Cell Count, Hemoglobin, Platelet Count, Absolute Neutrophil Count, Neutrophil Precursors (promyelocytes, myelocytes, metamyelocytes, band neutrophils), Lymphocytes, Monocytes, Blasts, and Reticulocytes.
- Coagulation panel: PT/INR, APTT
- Changes in vital signs: blood pressure, heart rate, temperature

Unless explicitly indicated otherwise, all analyses for safety will be based on the ASaT population.

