Overall view of TEAEs will be provided, which will include the total number of TEAEs, frequency of subjects with TEAEs, drug-related AEs, SAEs, drug-related SAEs, or death within 30-days within administration of study-drug; and AEs leading to permanent discontinuation of study drug. Additionally, a corresponding overall view of exposure-adjusted AE incidence will be provided, in which the exposure-adjusted incidence rate, is calculated as the mean number of events per treatment cycle, with corresponding 95% confidence intervals.

Summary tables will be provided which present the incidence of TEAEs by SOC and PT; and the incidence of TEAEs by SOC/PT by maximum severity (NCI-CTCAE Grades 1 through 5).

Summary tables will be provided which present the incidence of hematology-related TEAEs by SOC and PT; and the incidence of hematology-related TEAEs by SOC/PT by maximum toxicity grade.

A summary of the AE durations for all TEAEs by SOC/PT will be provided.

Summary tables will be provided which present the incidence of study-drug related TEAEs; and the incidence of study-drug related TEAEs severity scores of Grade 3 or higher.

Summary tables will be provided which present the incidence of SAEs by SOC/PT; and the incidence of TEAEs leading to permanent discontinuation of drug by SOC/PT.

Data on AEs will be presented in listings.

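### SAP 10.1 enters adverse events still ongoing at end of study as if they had resolved on an undefined last contact date, so the reported median AE duration can be too short or too long.

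*SAP*

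**What the plan says.** AE duration is a named safety measure. Protocol 12.2.2 lists "Incidence, duration, and severity of TEAEs, SAEs, AEs resulting in permanent discontinuation of study drug", and SAP section 10 repeats it.

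SAP 10.1 sets the method:

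- **Events included:** "AE durations will be calculated using all TEAEs", so resolved and unresolved events are pooled.
- **Unresolved events:** "For any AE that is still ongoing at the end of study", the SAP continues, "we will use the last contact date as the end of AE stop date for calculation the duration of AEs".
- **Statistic:** "Median, minimum and maximum of AE durations will be reported".
- **Output:** "A summary of the AE durations for all TEAEs by SOC/PT will be provided".

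Neither document marks these values as censored, asks for the number ongoing beside the median, or defines the last contact date. SAP section 13 leaves missing-data conventions to the section on each endpoint, so SAP 10.1 is the governing rule. By contrast, SAP 9.2 right-censors duration of response and summarises it by Kaplan-Meier.

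**The concern.** An event that has not resolved has a duration known only to exceed the time observed. Entering that time as a complete duration treats a lower bound as an observation. Long-lasting events, and events with little follow-up after onset, lose most.

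The assigned date has a second weakness. Under Protocol 10.9, AE reporting ends 30 days after the last dose or just before other anticancer therapy begins. Under Protocol 11.6.2, survival contact continues about every 12 weeks after progression, possibly by phone. A last contact can therefore fall well after anyone last checked whether the event had resolved, and the error then runs the other way.

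Duration has some clinical weight here. Protocol 9.4 gives too little recovery time from myelosuppression as the reason for the schedule change in Amendment 2, and says that the trial's data will inform the choice of dose and regimen.

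**Working it through.** **Plan's own figure.** Neither document gives an expected AE duration, a share of events ongoing or a follow-up distribution, so there is nothing to reproduce. All numerical inputs below are assumptions.

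**Step 1: direction when the event really is ongoing at the assigned date.** Let D be the true duration and C the time from onset to that date. The SAP records min(D, C), which never exceeds D, so the median can fall or stay the same but cannot rise.

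A ten-event example has six resolved durations of 3, 5, 7, 9, 12 and 14 days. With four ongoing events cut off at 2, 4, 6 and 8 days, the raw median is 6.5 and the Kaplan-Meier median is 9. With the four cut off at 60, 90, 120 and 150 days, the raw median is 13 and the Kaplan-Meier median 12. That gap is only the midpoint convention, because every ongoing event already lies above the median.

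**Step 2: size with at least 30 days of observation after onset.** Assume D is exponential with median M, and C = 30 + a uniform draw on (0, W) days. The 30 days reflects the post-dose reporting period in Protocol 10.9. The recorded value exceeds t with probability

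- 2^(−t/M) for t up to 30;
- 2^(−t/M) × [1 − (t − 30)/W] for t from 30 to 30 + W.

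Setting this to 0.5 gives the reported median:

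| True median M | W = 60 | W = 120 | W = 180 |
|---|---|---|---|
| 30 days | 30.0 (27% ongoing) | 30.0 (17%) | 30.0 (12%) |
| 60 days | 41.5 (51%) | 46.9 (38%) | 49.9 (30%) |
| 90 days | 46.9 (64%) | 57.0 (52%) | 63.4 (43%) |

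Check for M = 60, W = 60: 2^(−41.5/60) = 0.619, 1 − 11.5/60 = 0.808, product 0.500. For M = 30 the curve reaches 0.5 at exactly 30 days, before any event is cut off, so there is no bias. The shortfall is 17% to 31% at 60 days (49.9/60 and 41.5/60) and 30% to 48% at 90 days (63.4/90 and 46.9/90).

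**Step 3: other follow-up patterns.** If observation after onset can be arbitrarily short, with C uniform on (0, W), the same calculation gives 16–24 days for a true 30, 22–39 for a true 60 and 24–49 for a true 90. A simulation with onset uniform up to 30 days after 84, 168 or 365 days on treatment gave 31.9, 40.4 and 48.6 days for a true 60. Over 30 such scenarios (exponential and lognormal, true medians 14 to 240 days) the shortfall ran from 4% to 80%. Kaplan-Meier with censoring recovered the truth within about 1% wherever the median was reached.

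**Step 4: last contact later than the last AE assessment.** Let AE assessment end at 30 + uniform(0, 168) days after onset, with last contact 84 days later:

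| True median | Raw median, last contact | Kaplan-Meier, censored at last contact | Kaplan-Meier, censored at last AE assessment |
|---|---|---|---|
| 60 days | 64 | 64 | 60 |
| 90 days | 114 | 114 | 90 |

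The two middle columns agree because every unresolved event is placed at 30 + 84 = 114 days or later, so none leaves the risk set sooner. Censoring at the wrong date corrects nothing.

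**The case against.** The strongest reply is that this is a small descriptive table in a trial of about 36 subjects, with other safeguards.

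- Protocol 10.12 has the investigator follow possibly related events until stabilisation or known outcome, and the sponsor do the same for serious ones.
- Protocol 10.4 keeps most isolated laboratory abnormalities out of AE reporting, and SAP 10.2 summarises haematological toxicity from laboratory grades with a shift table. Recovery from myelosuppression does not rest mainly on AE durations.
- All AEs are listed individually.
- Kaplan-Meier within system organ class and preferred term will be sparse, and repeat events in one subject are not independent.

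All of this stands. It limits the consequence, and it is why the fix needs a fallback for small cells. It does not make a cut-off duration a complete one.

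A reader might also infer more than the documents support:

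- **That the median is certainly too low.** This needs the event to be ongoing at the assigned date and cut off before the true median. The undefined last contact date leaves the opposite error open.
- **That a true 30-day median would be reported as 16–24 days.** This needs observation after onset that can start from zero. Protocol 10.9 normally gives about 30 days after the last dose. Only events starting after that dose, or cut short by new therapy, death or withdrawal, have less.
- **That the regimen comparison is distorted.** SAP 10.1 shows the regimens separately in its AE tables, but no test of AE duration is planned and nothing indicates that follow-up will differ between them.
- **That the SAP already censors such events elsewhere.** SAP 7.5 says "For survival analysis, dropouts without confirming events will be treated as censored". That concerns dropouts in survival analysis. Duration of response in SAP 9.2 is a fair analogy, but it is not a rule for AEs.

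**Conclusion.** The point holds as a minor one. SAP 10.1 analyses unresolved AEs as complete, at a date it does not define. Where the event was truly ongoing at that date, the bias is downward or nil; where the date falls after AE assessment ended, durations may be overstated. The size is not determined by the documents. The figures in Step 2 of the working rest on exponential durations, a 30-day minimum of observation and assumed follow-up widths. They show no effect for short events and a material one for long events. The reported maximum is affected as well. Overall response rate, the stage 1 decision and AE incidence are untouched.

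**What to change.** In SAP 10.1:

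1. Replace the last contact date with the last date on which the status of that AE was assessed, and define it.
2. Treat events ongoing at that date as right-censored.
3. Report the number of events and the number ongoing, with a Kaplan-Meier median.
4. Where a cell by system organ class and preferred term is too small, summarise resolved and ongoing events separately.

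The cost is a few sentences and a method the SAP already uses for duration of response; the assessment date must be derivable from the AE records. Some medians will not be reached and sparse cells will be imprecise. Listings do not change.

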10.4 Abnormal Laboratory Findings and Other Abnormal Investigational Findings

Abnormal laboratory findings and other abnormal investigational findings (e.g. on an ECG trace) should not be reported as AEs unless they are associated with clinical signs and symptoms, lead to treatment discontinuation or are considered otherwise medically important by the Investigator. If an abnormality fulfills these criteria, the identified medical condition, e.g. anemia, increased alanine aminotransferase (ALT), must be reported as the AE rather than the abnormal value itself.

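### The SAP's list for pooling laboratory-coded hematologic AEs has no hemoglobin/anemia pair, so anemia may be under-counted if any AE is coded as a hemoglobin decrease

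*SAP*

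**What the plan says.** SAP 10.1 (Adverse Events) sets the rule, whose target is the Blood and Lymphatic class: "Hematologic abnormalities reported as AEs that were coded to preferred terms in the Investigations SOC have been pooled with appropriate terms in the Blood". The rule covers a stated set of categories, which are:

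- "Platelet count decreased = Thrombocytopenia"
- "Neutrophil count decreased = Neutropenia"
- "White blood cell count decreased = Leukopenia"
- "Lymphocyte count decreased = Lymphopenia"

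The list ends there. Nothing marks it as a set of examples, and the absence of a hemoglobin line is not explained.

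The same section fixes the counting unit: "A subject reporting multiple cases of the same AE will be counted once within each SOC and similarly counted once within each PT".

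Protocol 12.2.2 groups three toxicities: "The incidence of grade 3 and 4 hematological toxicities (including neutropenia, thrombocytopenia, and anemia"). Protocol 10.4 tells sites how to report a laboratory abnormality that qualifies as an AE: "the identified medical condition, e.g. anemia, increased alanine aminotransferase (ALT), must be reported as the AE rather than the abnormal value itself".

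**The concern.** A pooling rule exists so that one clinical problem is not spread over two preferred terms in two system organ classes because of the words a site happened to use. SAP 10.1 does this for two of the three hematological toxicities named in the protocol and leaves out the third. If a site records a fall in hemoglobin and it is coded under Investigations, that record stays there. The equivalent platelet or neutrophil record is moved.

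The anemia row could then be too low, overall and by regimen, and the comparison between cytopenias would be uneven. The tables exposed are those that SAP 10.1 builds on SOC and PT: incidence, maximum severity, hematology-related events, durations, SAEs and events leading to permanent discontinuation. Anemia is a common event in this setting. Protocol 9.4 reports it in 34% of subjects in the earlier phase 2 study of 300 mg bid on the 3 weeks on/1 week off schedule, against thrombocytopenia in 41% and granulocytopenia in 29%.

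**Working it through.** The plan gives no figure to reproduce. The check is a comparison of texts followed by an illustration of size.

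**Step 1. Coverage of the list.** The hematology panel is in SAP 10, the named toxicities in Protocol 12.2.2 and the pairs in SAP 10.1.

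| Parameter | In the panel | Named toxicity | Pooling pair |
|---|---|---|---|
| Platelets | yes | thrombocytopenia | yes |
| Neutrophils | yes | neutropenia | yes |
| White cells | yes | no | yes |
| Lymphocytes | yes | no | yes |
| Hemoglobin | yes | anemia | **none** |
| Monocytes, reticulocytes | yes | no | none |

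Hemoglobin is the only parameter that corresponds to a named toxicity and has no pair. It is not the only panel parameter without one.

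**Step 2. What the counting rule does.** Each subject counts once per PT and once per SOC. Without a pair, three cases arise:

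- Anemia term only, or both terms: the subject is in the anemia row. With both terms, the grade shown for anemia could be too low if the hemoglobin record carries the higher grade.
- Hemoglobin-decrease term only: the subject is missing from the anemia row, and also from the Blood SOC row unless another Blood event is present.
- No hemoglobin-decrease term in the database: nothing changes.

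**Step 3. Illustrative size.** Inputs:

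- p = 34%, the anemia AE frequency in the earlier study (Protocol 9.4), borrowed as an assumption.
- N = 18 per regimen, or 36 in all, if both cohorts complete stage 2.
- f = share of subjects with an anemia event who have only the hemoglobin-decrease term. The documents do not give f; the range 0 to 50% is assumed.

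Formulas: displayed rate = p(1 − f); subjects missing = N × p × f; chance of at least one missing subject = 1 − (1 − pf)^N, treating subjects as independent.

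| f | Displayed rate | Missing of 18 | Chance of ≥1 in 18 | Missing of 36 | Chance of ≥1 in 36 |
|---|---|---|---|---|---|
| 0 | 34.0% | 0 | 0 | 0 | 0 |
| 5% | 32.3% | 0.31 | 0.266 | 0.61 | 0.461 |
| 10% | 30.6% | 0.61 | 0.463 | 1.22 | 0.712 |
| 20% | 27.2% | 1.22 | 0.718 | 2.45 | 0.921 |
| 50% | 17.0% | 3.06 | 0.965 | 6.12 | 0.999 |

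Worked line for f = 10%: 0.34 × 0.90 = 30.6%; 36 × 0.34 × 0.10 = 1.22; 1 − (1 − 0.034)^36 = 0.712. One subject in a cohort of 18 is 1/18 = 5.6 percentage points. With the pair added, the displayed rate returns to p in every line.

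**The case against.** The strongest reply is that there may be nothing to pool. Neither document shows an AE coded to a hemoglobin term under Investigations. Protocol 10.4 gives anemia as its first example of a condition to be reported in place of the value. SAP 10.1 is also written in the past tense, so the list may simply record the terms found in the coded data. This stands as a reason for conditional wording, but it does not close the point. The Protocol 10.4 instruction covers the other lineages too, and the SAP still provides for laboratory-coded terms there. If the list is a record of what was found, the SAP does not say so.

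The second reply is that little is exposed, and most of this stands. A hemoglobin-coded AE would still appear in its own SOC/PT row, in total TEAE counts and in the listings. SAP 10.2 summarizes Grade 3 or above hematological toxicities and shifts to worst grade from laboratory evaluations, independently of AE terms. The Protocol 12.2.2 sentence on grade 3 and 4 toxicities is followed by a rule for grading laboratory tests, so it supports the importance of anemia more than any particular AE table. The laboratory tables do not, however, give seriousness, duration or discontinuation for anemia as an AE.

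A reader might go on to infer that hemoglobin bears on efficacy here and that the pooling gap therefore reaches the endpoints. It does not. RBC transfusion independence is defined in Protocol 12.2.1 and SAP 9.2 from transfusion records and hemoglobin values, and response from the IWG criteria; AE coding enters neither.

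**Conclusion.** The omission is real and unexplained. Its consequence is conditional: anemia AE incidence may be under-counted relative to the pooled cytopenias, in the anemia PT row and in the Blood SOC row for subjects with no other Blood event.

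It is tempting to say that anemia is split and understated, and that it alone is treated this way. The documents support neither. The first depends on coding they do not report, and monocytes and reticulocytes also lack a pair.

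The under-count is zero if no hemoglobin-decrease term is used. Under the borrowed 34% rate it would be 3.4 percentage points at f = 10% (34.0% to 30.6%) and 17 points at f = 50%. The upper end would need half of the subjects with anemia to have only the laboratory term despite Protocol 10.4, so it is a bound for the illustration and not an expectation. No decision rule in the plan uses the anemia AE row. This is a minor point, worth making because the correction costs almost nothing.

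**What to change.** Add a fifth pair to the list in SAP 10.1: 'Haemoglobin decreased = Anaemia', spelled to match the MedDRA version in use. Apply it in the SOC/PT, maximum-grade, hematology-related, duration, SAE and discontinuation tables. Counting once per PT after the recode means that a subject with both terms is still counted once.

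If the coded data contain no such term, a sentence in SAP 10.1 saying so would explain the omission; the added pair would do no harm in that case.

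The cost is one line in the SAP and one recode in programming. The anemia rate may read slightly higher. No efficacy or laboratory table changes.
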